#### Arterial stiffness as alternate CV risk indicator

Apart from FRS, arterial stiffness was suggested to be an alternative measurement of CV risk. An increase in aortic PWV by 1 SD corresponds to an age-, sex- and risk factor-adjusted risk increase of 47%, 47% and 47% in total cardiovascular events, cardiovascular mortality and all-cause mortality, respectively.(26) Alx has emerged as a surrogate marker for CVD. A 10% increase of central Alx is associated with a relative

risk of 1.4 for all-cause mortality.(27) Therefore, arterial stiffness measurement could serve for additional CV risk indication apart from FRS and/or subclinical carotid atherosclerosis by ultrasound.

#### Intervention of CV risk in the nurse-led clinic

All patients will receive a one-on-one nurse-led intervention at baseline and month 12 including:

- (1) Detection of CV risk factors (eg, hypertension, diabetes, hypercholesterolaemia).
- (2) Calculation of the FRS. We will follow the recommendation to adapt for patients with RA by a 1.5 multiplication factor (5).
- (3) The implementation of the recommendation for the detection (eg, yearly evaluation of CV risk factors) and/or management of such comorbidities at baseline. Nurses will be given a booklet to be used for the systematic identification and assessment of the comorbidities associated with RA and PsA. In case of a detected risk factor (eg, hypertension) and/or a non-optimally managed comorbidity (eg, Hba1c > 7), the nurse reminds the patient the interest of the management of such comorbidity and advises the patient to visit her/his general practitioner and/or rheumatologist to take care of it. In parallel, a report of this visit will be given to the patient to hand-over to the rheumatologist of each evaluated patient during their next clinical visit.
- (4) The report of the presence of newly developed CV comorbidities at month 12.
- (5) The number of new measures taken against comorbidities at month 12. The following measures against comorbidities are considered for the definition of the secondary objective of the trial: purchase of BP self-measurement devices, attending education class by dietitian and initiation of a diet because of overweight +/- hyperlipidemia, smoking cessation, initiation of lipid-lowering therapy, initiation of antiplatelet therapy, referral to a nephrologist because of renal insufficiency (chronic kidney disease stage IIIb).
- (6) adherence of lipid-lowering and antiplatelet therapy at month 12.

#### Carotid intima-media thickness (IMT) and plaque

All patients will have the carotid intima-media thickness (IMT) and plaque assessed at baseline and 12 months at the Prince of Wales Hospital. Carotid IMT will be measured using a high-resolution B-mode ultrasound machine (Philips EPIQ7). Briefly, duplex carotid ultrasound will be performed by an experienced sonographer blinded to all clinical information using a 30-MHz linear vascular probe (Philips L12-3 broadband linear array transducer). The IMT will be measured offline in the distal common carotid artery (the arterial segment 1 cm proximal to the carotid bulb), bulb, and proximal internal carotid artery (the arterial segment 1 cm distal to the carotid bifurcation) using dedicated software (Philips Xcelera Cardiology Enterprise Viewer Client 4). The values of maximal thickness will be recorded, not including plaques, for the following calculation. Plaque is defined as a localized thickening >1.2 mm that do not uniformly involve the whole artery. The mean and maximal IMT values of 6 arterial segments will be calculated for further analysis. Reproducibility of IMT in our center was 0.97 (13).

A report of this visit will be given to the patient to hand-over to the treating rheumatologist during their next clinical visit. All participating rheumatologist will attend a briefing session on the importance of carotid ultrasound screening and the risk represented by carotid plaque in order to avoid under-appreciation of CV risk. Moreover, while the results of the US scan will be provided to the patient's primary rheumatologist, an interpretation of the findings regarding level of CV risk will also be provided.

#### Pulse wave velocity (PWV) and pulse wave analysis (PWA)

Arterial stiffness will be measured by baPWV, cfPWV and Alx at baseline and month 12 for all subjects(28). Participants receive PWA examination in the morning, having fasted overnight; having a light meal 4h before measurement and avoid tobacco, alcohol, and caffeine with 3h before measurement. Participants rest in sitting position in a quiet room for at least 10 minutes before examination. BP is measured 3 times at the right brachial artery using a validated oscillometric device (Omron HEM-757 - UK). PWA is performed using the pressure cuff and analog system (VICORDER Version 3.1 - UK). The central aortic arterial pulse wave is transferred from the peripheral arterial pulse wave automatically. Since Alx in an individual patient varies by heart rate, it is standardized to a heart rate of 75 beats-per-minute (b.p.m.) (Alx@75).

Carotid femoral PWV (cfPWV) is a gold standard of arterial stiffness and will be measured by VICORDER system as well. cfPWV will be measured in the supine position by a sphygmomanometer cuff in bilateral carotid and femoral position. The VICORDER machine measures and records results of pulse waveforms

of carotid and femoral arteries automatically. cfPWV is defined as the mean speed of bilateral blood pressure wave traveling between carotid and femoral artery. The distance between sampling points are measured manually.

Brachial-ankle PWV (baPWV) is another measure of arterial stiffness and will be assessed non-invasively in subjects in the supine position by a dedicated tonometry system (Non-Invasive Vascular Profile Device VP-2000; Omron Healthcare, Inc. Bannockburn, Illinois, USA). In brief, this device record PWV, blood pressure, electrocardiogram (ECG), and heart sounds simultaneously. Sphygmomanometer cuffs are applied on both arms just above the level of elbows and on both legs just above the ankles. ECG electrodes are placed on both wrists, and a heart sound microphone is placed on the left sternal border. The machine measures and records results of electrocardiogram, phonocardiogram and blood pressure of limbs as well as pulse waveforms of carotid and limb arteries automatically. baPWV is defined as the speed of the blood pressure wave traveling between brachium and ankle. The distance between sampling points of brachial-ankle PWV are calculated automatically according to the height of the subject. All PWA measurements are made by a single skilled operator. Intra-observer reliability is 0.86 (28). The reports will also be hand over to the attending rheumatologist in their subsequence visit, and to further evaluate the CV risk.

#### **Treatment protocol**

There are no formal guidelines on the management of patients with high CV risk or identified carotid plaque in Hong Kong. The following management plan was formulated after a general discussion with practicing rheumatologists and cardiologists locally.

#### Use of statins

Group 1 patients will be prescribed statin when FRS > 10%; while group patients will be prescribed statin upon presence of carotid plaque as reported from carotid ultrasound. The decision will solely be made base on the randomized group by either FRS>10% or presence of carotid plaque.

We choose atorvastatin 20 mg daily since generic atorvastatin is available in the Hong Kong Hospital Authority drug formulary. Each tablet cost HK \$ 0.28 and the yearly cost is HK \$ 102.2 (around US \$ 13) per person. Atorvastatin 20 mg is recommended as the preferred initial high-intensity statin to use because it is clinically and cost effective for the primary prevention of CVD according to the national institute for Health and Care Excellence (NICE) guideline from the United Kingdom. Nonetheless, similar data is lacking in Hong Kong.

No trials to date that have evaluated effects on CVD events have tested any medication in combination with statins or treatment to specific LDL-C goals, therefore we do not intensify the regimen for any particular level of LDL-C response. Measuring LDL-C response after initiating therapy in this study is mainly to assess adherence. In this primary prevention trial, in patients who do not tolerate statins, no lipid-lowering therapy will be administered. Potential interventions include lifestyle modification and, in higher-risk patients, antiplatelet therapy.

#### Use of Aspirin

For low-risk patients (ie, men and women whose 10-year absolute risk of a first coronary heart disease event is <10 percent), the absolute benefit of a reduction in CV events is unlikely to exceed the absolute risk of major bleeding. For moderate- and high-risk patients (ie, men and women whose 10-year absolute risk of a first CVD event is  $\geq 10$  percent), randomized data on benefits and risks are sparse. Nonsteroidal anti-inflammatory drug (NSAID) therapy combined with aspirin use increases the risk for serious gastrointestinal (GI) bleeding compared with aspirin use alone (29). The gastrointestinal harms may offset the CV benefits in our group of patients on long-term NSAID where the GI risk is high and the CV risk is low. Therefore, aspirin for primary prevention in this trial will be highly individualized based on a benefit/risk ratio assessment for each patient and a clinician-patient discussion regarding potential benefits, potential harms, and patient preferences.

#### Use of DMARDs

Disease activity should be controlled optimally in order to lower CVD risk in all patients with RA or PsA (5). All participants will receive a 1-year protocolized treatment (Appendix 2 and 3) with the aim to achieve remission. The protocol was developed based on the EULAR recommendations, the Hong Kong Society of Rheumatology recommendation and the Hong Kong guideline for the use of biologics. When patient cannot achieve treatment goal within 3 to 6 months of therapy, the treatment therapy will be escalated to the next step according to the protocol, unless the patient declined or toxic effects preclude this approach.

### Toxicity monitoring

To monitor the possible side effect of the NSAID, biologic and synthetic DMARDs, statins and aspirin, patients will be asked about various symptoms (such as myalgias or weakness for statins; coffee ground vomiting, melaena and dyspepsia for NSAID and aspirin). Complete blood count, liver function tests and renal function tests will be performed during every clinic visit. Creatinine kinase will be measured in patients who complain of myalgias or weakness after starting statins. Chest X-rays will be obtained at baseline and at the end of the study. The treating physician record all adverse events and serious adverse events and, if necessary, make treatment adjustments in accordance with the protocol. Serious adverse events are defined as any adverse reaction resulting in any of the following outcomes: a life-threatening condition or death, a significant or permanent disability, a malignancy, hospitalization or prolongation of hospitalization, a congenital abnormality, or a birth defect.

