### Trial design

This is a 1-year prospective, hospital-based, open-label, randomized, controlled trial. The trial comprised two arms. Both group will participate in the nurse-led programme on CV risk screening and carotid ultrasound for carotid plaque assessment. Subjects in group 1 will initiate statin treatment if their Framingham Risk Score >10%; while subjects in group 2 will initiate statin treatment if they had carotid plaque upon carotid ultrasound findings.. (Appendix 1). The method of concealed random allocation will

be used. Simple randomization will be conducted by a computer-generated random list. Randomisation will be centralized for all centres. Information on each patient's allocated treatment will be recorded in the clinical report form (CRF) and also entered into the patient's computerized medical record (CMS) by the nurse. The study will be approved by the respective Ethics Committees of each hospital and all patients will provide written consent.

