### **Outcome measures**

The primary outcome is the change in FRS. Although this algorithm was developed for prediction of absolute coronary risk among patients without clinical manifestations of CAD, they combine the following major risk factors recognized for coronary and other atherosclerotic CVD (ASCVD): age, sex, high BP, smoking, dyslipidemia, and diabetes status. We use risk scores as a composite measure of change in modifiable major risk factors, rather than as a predictor of risk. This approach has been previously used in evaluating effects of nurse- and dietitian-led case management program to reduce CV risk (30). Baseline age will be applied when calculating the FRS at 12 months.

Secondary end points included

- 1) Change in arterial stiffness in subjects
- 2) Change in individual modifiable risk factors (systolic and diastolic BP; TC, LDL-C, HDL-C and TG levels; TC/HDL ratio; and hemoglobin A1c value in patients with diabetes)
- 3) The number of measures taken against comorbidities.
- 4) Proportions of patients achieving remission.
- 5) Changes in IMT and proportion of plaque progression in subjects between 2 groups

The trial will be conducted with compliance to ICH-GCP and Declaration of Helsinki.

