**Sample size calculation:**

The sample size is estimated by the Power Analysis and Sample Size for Windows software (PASS 2000, NCSS, Utah, USA). All calculations will use a two-sided  $\alpha$  of 0.05 and  $\beta=0.2$  achieving 80% power. From our previous cohort study, standard deviation of FRS was 8. Taking population variance of FRS as 64, and suppose 4 unit drop in FRS is clinically meaningful. A sample size of 63 is required in each group. Assuming a drop-off rate of 10%, a total sample size of 140 (i.e. 70 per arm) would be sufficient.

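### The protocol defines a serious adverse event as an adverse reaction, so a serious event attributed to no drug is recorded but not classed as serious

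*Protocol*

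**What the plan says.** Everything that bears on the definition is in the protocol's Toxicity monitoring section. It opens with its purpose: "To monitor the possible side effect of the NSAID, biologic and synthetic DMARDs, statins and aspirin". It then sets the recording duty: "The treating physician record all adverse events and serious adverse events". The next sentence gives the definition: "Serious adverse events are defined as any adverse reaction resulting in any of the following outcomes". The outcomes listed are a life-threatening condition or death, significant or permanent disability, malignancy, hospitalisation or its prolongation, congenital abnormality and birth defect.

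Three other places supply the setting:

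- Trial design: "This is a 1-year prospective, hospital-based, open-label, randomized, controlled trial". The same section has the nurse enter each patient's allocation in the report form and in the computerised medical record.
- Use of statins, on who starts the drug: "The decision will solely be made base on the randomized group by either FRS>10% or presence of carotid plaque".
- Outcome measures, closing line: "The trial will be conducted with compliance to ICH-GCP and Declaration of Helsinki".

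The protocol does not define an adverse reaction. It contains no second definition of a serious adverse event, no causality assessment, and no statement that relatedness is irrelevant to seriousness.

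**The concern.** Two consecutive sentences use different terms. What is recorded is an event; what counts as serious is a reaction. An event is anything untoward that happens to the patient. A reaction is something a drug is thought to have caused. The second sentence therefore adds a causal condition to seriousness, and the protocol neither explains that condition nor provides for it to be assessed or documented.

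Two things are at stake. The first is oversight. Serious events are the ones a trial singles out for attention, and under this wording a death or admission attributed to no drug is not among them. The second is the meaning of any count of serious events by arm. The causal judgement falls to a treating physician who can see the allocation, and the arms differ in which patients start a statin. A patient not taking a statin cannot have a statin reaction, so the condition is not neutral with respect to allocation.

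**Working it through.** The point is about wording. The protocol's one design calculation was checked first, to confirm that nothing in it depends on the definition.

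**Sample size (context only).** Inputs from Sample size calculation: two-sided α of 0.05, 80% power, a difference of 4 FRS units, and "standard deviation of FRS was 8".

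- n per arm = 2 × (1.960 + 0.842)² × 8² / 4² = 2 × 7.85 × 4 = 62.8, rounded up to 63.
- With 10% drop-off: 63 / 0.90 = 70 per arm, 140 in total.
- Power at 63 per arm: 0.801.

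The stated figures reproduce. None of them uses a safety definition.

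**The sentences applied literally.** An event is classed as serious if it is (i) an adverse reaction and (ii) has a listed outcome. It is recorded if it is an adverse event of any kind. Applied to four cases:

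1. *Admission with infection, attributed to a biologic DMARD.* Recorded: yes. Serious: yes. It is a reaction to a monitored drug with a listed outcome.
2. *Admission for gastrointestinal bleeding, attributed to an NSAID or aspirin.* Recorded: yes. Serious: yes, for the same reason.
3. *Admission for a first cardiovascular event, attributed to the underlying disease or a comorbidity.* Recorded: yes. Serious: no. Condition (ii) holds but condition (i) fails.
4. *Malignancy or death attributed to no drug.* Recorded: yes. Serious: no.

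The gap is therefore cases 3 and 4: events with a listed outcome that the physician attributes to nothing the patient was taking. Case 3 is relevant to this population. Overt cardiovascular disease is an exclusion criterion, so a cardiovascular admission during the year would be new.

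**Who decides.** Under Treating rheumatologists, these physicians manage the patients. Under Toxicity monitoring, the treating physician records the events. Under Trial design, treatment is open and allocation is in the medical record. Since no causality field is specified, the judgement would be made implicitly when the event is labelled and would leave no trace. A later reader could not tell whether an event was left out of the serious category because its outcome was not listed or because it was thought unrelated.

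**Size.** The number of events affected is the number with a listed outcome multiplied by the share attributed to no drug. The document gives neither quantity, so no figure or range can be derived from it.

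**The case against.** The best reply is that *reaction* is simply loose wording for *event*. The section moves between the terms in consecutive sentences, sets up no relatedness assessment and never defines a reaction, so a sensible site might class every listed outcome as serious. That reading is plausible, but nothing in the protocol confirms it. The section's stated purpose, monitoring drug side effects, makes the narrow reading at least as natural. A definition that two sites can apply differently still needs correcting.

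The reply is stronger against larger conclusions that a reader might draw:

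- *That unrelated serious events go unrecorded.* They do not. The sentence before the definition requires all adverse events to be recorded, so what is lost is the classification as serious.
- *That admissions attributed to DMARDs are lost.* They are not. DMARDs are among the monitored drugs, and the definition is not limited to statin reactions.
- *That a planned safety comparison between arms is biased and might be reversed.* Neither Outcome measures nor Statistical analysis specifies a comparison of serious events by arm. The concern extends only to a tabulation that someone might later make, and no event rate is given from which to judge a reversal.
- *That the definition contradicts the commitment to ICH-GCP.* The protocol does not reproduce the definitions of that standard, so the point is not rested on it.

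The nurse-led clinic also reports newly developed cardiovascular comorbidities at month 12, which would pick up some of the same events. That report does not assign seriousness, and it does not cover non-cardiovascular deaths, admissions or malignancies.

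**Conclusion.** The definition is wrong as written. It makes seriousness conditional on a drug cause, disagrees in its terms with the sentence before it, and leaves the causal judgement to a physician who can know the allocation. The consequence is limited: an event with a listed outcome that is attributed to no drug is kept as an adverse event but not classed as serious. That weakens safety oversight, and it would make any later count of serious events by arm depend on open-label opinion. The primary and secondary endpoints, the sample size of 140 and every analysis the protocol describes are untouched.

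The conclusion assumes that sites apply the words as they stand. If every site read *reaction* as *event*, nothing would be lost in practice, but the protocol gives no assurance of that. The point also does not belong to a later analysis plan. The definition governs how events are labelled when they occur, and seriousness may not be recoverable afterwards if causality was built into the label.

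**What to change.** In Toxicity monitoring, replace *any adverse reaction* in the definition with *any adverse event, whether or not considered related to study treatment*. Leave the list of outcomes as it is. Add a separate causality field to the event form, so that the physician's opinion is recorded without deciding whether the event counts as serious. Related serious events can then still be reported as a subset of all serious events.

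The cost is one phrase in the protocol, one field on the form and slightly more SAE forms. No treatment rule, endpoint, sample size or analysis changes.

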### **Outcome measures**

The primary outcome is the change in FRS. Although this algorithm was developed for prediction of absolute coronary risk among patients without clinical manifestations of CAD, they combine the following major risk factors recognized for coronary and other atherosclerotic CVD (ASCVD): age, sex, high BP, smoking, dyslipidemia, and diabetes status. We use risk scores as a composite measure of change in modifiable major risk factors, rather than as a predictor of risk. This approach has been previously used in evaluating effects of nurse- and dietitian-led case management program to reduce CV risk (30). Baseline age will be applied when calculating the FRS at 12 months.

Secondary end points included

- 1) Change in arterial stiffness in subjects
- 2) Change in individual modifiable risk factors (systolic and diastolic BP; TC, LDL-C, HDL-C and TG levels; TC/HDL ratio; and hemoglobin A1c value in patients with diabetes)
- 3) The number of measures taken against comorbidities.
- 4) Proportions of patients achieving remission.
- 5) Changes in IMT and proportion of plaque progression in subjects between 2 groups

The trial will be conducted with compliance to ICH-GCP and Declaration of Helsinki.

**Statistical analysis:**

Descriptive statistics will be used for demographic and clinical variables included frequencies, percentage, means and standard deviations, median and interquartile range. Comparisons in demographic and clinical characteristics at baseline will be performed using chi-square test, independent samples *t*-test or Mann-Whitney *U* test, depending on distribution of data. We will compare the proportion of participants eligible for statin treatment using FRS >10% vs carotid ultrasound criteria using the McNemar test. The intervention effect on the primary and secondary outcomes will be examined at 12 months on an intention-to-treat basis using a mixed-effects regression model adjusted for baseline FRS. The model will also take into account random effects associated with physicians and clinics in a hierarchical structure. The magnitudes and patterns of missing data will be examined by the randomized group. Missing outcomes at the 12-month follow-up will be imputed using the method of the baseline observation carried forward. The same mixed-effects model will be used for subgroup analyses defined by sex and underlying diseases. All statistical analyses will be conducted using IBM SPSS Statistics Version 23 (IBM, Armonk, NY, USA). A level of significance of *p* =0.05 is used.

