#### Cardiovascular assessments

The following anthropomorphic assessment will be performed for all patients at baseline and at the end of the study. Anthropomorphic measurements include body heights, body weight, waist and hip circumferences, two consecutive blood pressure (BP) readings in sitting position and heart rate. Hypertension status is defined as systolic blood pressure (SBP)  $\geq 140$  mmHg or diastolic blood pressure (DBP)  $\geq 90$  mmHg or the use of antihypertensive agents. Other data collected at baseline include menopausal status, smoking and drinking habits, social economic status, history of diabetes, hypertension, hypercholesterolemia, dyslipidemia, overt CVD and cerebrovascular diseases, peptic ulcer disease and family history of CVD, diabetes and cerebrovascular diseases in first-degree male relatives  $< 55$  years of age or first-degree female relatives  $< 65$  years of age. Drug history is retrieved from case notes or elicited during the clinical assessment. Body weight and blood pressure will also be measured during each visit to the rheumatologist.

Laboratory assessment at baseline include fasting blood glucose, fasting lipid profile (total cholesterol [TC], low-density lipoprotein-cholesterol [LDL-C], high-density lipoprotein-cholesterol [HDL-C], triglycerides [TG]), fibrinogen, thyroid function test, creatinine kinase and uric acid. Fasting sugar and lipid profile will also be measured at 6 and 12 months. Hemoglobin A1c levels will be measured at baseline and 12 months for patients with known diabetes.

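### Baseline FRS is the only baseline covariate named for the continuous secondary change outcomes; adding each outcome's own baseline, already collected, would give a modest gain in precision

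*Protocol*

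**What the plan says.** The protocol, Statistical analysis, sets one model for every endpoint: "primary and secondary outcomes will be examined at 12 months on an intention-to-treat basis using a mixed-effects regression model adjusted for baseline FRS". The only other terms named are random effects for physicians and clinics. For missing data, "Missing outcomes at the 12-month follow-up will be imputed using the method of the baseline observation carried forward".

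Under Outcome measures, the primary outcome is the change in FRS. The continuous secondary outcomes are also changes: arterial stiffness, IMT, and "Change in individual modifiable risk factors (systolic and diastolic BP; TC, LDL-C, HDL-C and TG levels", followed by the TC/HDL ratio and, in patients with diabetes, HbA1c.

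The baselines are scheduled. Cardiovascular assessments takes blood pressure at baseline and study end. For lipids it states "Laboratory assessment at baseline include fasting blood glucose, fasting lipid profile" and "Fasting sugar and lipid profile will also be measured at 6 and 12 months". The carotid and pulse wave sections schedule IMT and arterial stiffness at baseline and month 12 for everyone. HbA1c is measured only in patients with known diabetes.

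On allocation, Trial design states: "Simple randomization will be conducted by a computer-generated random list".

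**The concern.** For the change in FRS, baseline FRS is the outcome's own baseline. For the other change outcomes it is only a correlate. A change score subtracts the own baseline with a fixed slope of 1. When the baseline-to-12-month correlation is below 1, the change is negatively correlated with that baseline (regression to the mean). An arm that starts higher by chance will therefore tend to show a larger fall. Adjusting for FRS removes only the part of this that FRS shares with the outcome's baseline, and simple randomisation does nothing to limit such differences.

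At stake are the precision of these secondary comparisons and how far a chance imbalance moves the estimate in the one trial that is run.

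FRS is itself a sound covariate. The protocol says that the score combines "age, sex, high BP, smoking, dyslipidemia, and diabetes status", and it determines who receives a statin in group 1: "The decision will solely be made base on the randomized group by either FRS>10% or presence of carotid plaque". The question is whether to add to it, not whether to drop it.

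**Working it through.** **The plan's own figure.** With SD 8, difference 4, two-sided 0.05 and 80% power: 2 × (1.960 + 0.842)² × 64/16 ≈ 62.8, so 63 per arm; 63/0.9 = 70 per arm, 140 in total. This reproduces the protocol. No figure is given for any secondary outcome.

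**Inputs.** From the protocol: 70 per arm; 10% drop-off, with missing 12-month values replaced by baseline, so m = 0.10. Assumed, because the protocol does not give them: baseline-to-12-month correlation r = 0.5 to 0.9, and correlation q = 0.3 to 0.6 between own baseline and baseline FRS. The outcome is scaled to variance 1, and FRS is taken to relate to the 12-month value only through the own baseline.

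**Residual variance of the change, no statin effect.**
- FRS only: 2(1−m)(1−r) − [(1−m)(1−r)q]²
- Own baseline plus FRS: 2(1−m)(1−r) − [(1−m)(1−r)]²

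Example, r = 0.7 and q = 0.3: (1−m)(1−r) = 0.27. FRS only: 0.54 − 0.081² = 0.5334. Both: 0.54 − 0.27² = 0.4671. The ratio is 1.142. The extra covariate costs one degree of freedom (136/137 ≈ 0.993), which leaves 1.134.

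| r | FRS only, q = 0.3 / 0.6 | Own + FRS | Ratio after the factor | Simulated ratio |
|---|---|---|---|---|
| 0.5 | 0.8818 / 0.8271 | 0.6975 | 1.255 / 1.177 | 1.24 / 1.17 |
| 0.7 | 0.5334 / 0.5138 | 0.4671 | 1.134 / 1.092 | 1.13 / 1.10 |
| 0.9 | 0.1793 / 0.1771 | 0.1719 | 1.035 / 1.023 | 1.04 / 1.03 |

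The simulation used 70 per arm, 20,000 runs per cell, and ordinary regression without the physician and clinic random effects. Taking square roots, the FRS-only standard error is about 8-12%, 4-6% and 1-2% larger. The mean error of every estimator was at most 0.0023 SD, so none is biased.

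**Lipids.** Statin use depends on FRS in group 1 and on plaque in group 2. With an assumed statin effect of 1.2 SD, 40% eligible by either rule and an FRS-plaque correlation of 0.4, the simulated ratios were 1.12-1.18 (r = 0.5), 1.06-1.09 (r = 0.7) and 1.01 (r = 0.9). In the same setting, own baseline without FRS had 1.055 to 1.167 times the variance of both together, so FRS should stay.

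**IMT and arterial stiffness.** The protocol gives IMT reproducibility of 0.97 and intra-observer reliability of 0.86 for pulse wave measurements. These are not 12-month correlations, and the true r may be lower. If r equalled them, the same formula gives a standard error only 0.1-0.3% larger at 0.97 and 1.8-2.7% larger at 0.86.

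**Chance imbalance.** The standard error of the own-baseline difference is √(2/70) = 0.169 SD. The FRS-only estimate moves by −(1−m)(1−r)(1−q²) per unit of imbalance: −0.41 to −0.29, −0.25 to −0.17 and −0.08 to −0.06 at r = 0.5, 0.7 and 0.9. A one-standard-error imbalance thus shifts it by 0.05-0.07, 0.03-0.04 and about 0.01 SD. At r = 0.7 and q = 0.3 that is 0.2457 × 0.169 = 0.0415 SD, against a standard error with both covariates of √(0.4671 × 2/70) = 0.1155, or 36% of it.

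**HbA1c.** The number of patients with diabetes is not given. As an illustration with complete data, q = 0.3 and a small-sample factor of 1 + 1/(n−6), the variance with both covariates relative to FRS only is:
- n = 10: (0.51/0.5919) × 1.25 = 1.08 at r = 0.7, and (0.19/0.1991) × 1.25 = 1.19 at r = 0.9
- n = 14: 0.97 and 1.07

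Above 1, the extra covariate loses precision.

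**The case against.** The strongest reply is that nothing here is invalid. A change score adjusted for a prespecified prognostic covariate is a sound randomised comparison, and these endpoints are not powered. A statistical analysis plan, not shown, could add covariates without contradicting the protocol, which does not say that FRS is the only one. The size also rests on correlations that the protocol does not supply, and at the favourable end it is close to nothing.

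Most of that stands, and it is why the point is minor. It does not remove the point: the protocol does not leave the covariate open. It names one and applies it to the secondary outcomes, while the better baseline is already collected.

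A reader might infer more than the document supports:
- **Bias, or a threat to the primary result.** Neither follows. Randomisation protects the comparison on average, and the primary outcome already has its own baseline in the model.
- **A much larger loss, if 12-month values are modelled.** With FRS alone, adding own baseline would then cut the variance by about 47% at r = 0.7 and q = 0.3 (0.956 to 0.510). But Outcome measures defines these endpoints as changes, and the reference to 12 months can be read as timing.
- **FRS is the wrong covariate and should be replaced.** The lipid simulation shows that dropping it loses precision.
- **The own baseline helps every continuous outcome at no cost.** HbA1c may be an exception.

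**Conclusion.** The point holds as a minor matter of efficiency. It covers arterial stiffness, systolic and diastolic blood pressure, TC, LDL-C, HDL-C, TG, TC/HDL ratio and IMT. For these, the named adjustment gives up a modest amount of precision: a standard error up to about 12% too large if r is 0.5, and 1-2% if r is 0.9. It also lets part of a chance baseline difference into the estimate. The loss is smaller for lipids under the assumed statin effect, and perhaps negligible for IMT.

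The range depends on the assumed r and q, and the lipid figures also on the assumed statin effect, eligibility and FRS-plaque correlation. All of the calculations omit the random effects. Nothing is claimed for HbA1c, the number of measures taken, remission or plaque progression.

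**What to change.** In the protocol's statistical analysis section, or in the analysis plan before the data are analysed, write:

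> The primary outcome is adjusted for baseline FRS. Each continuous secondary change outcome measured in all patients is adjusted for its own baseline value in addition to baseline FRS.

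Keep FRS in every one of these models. Do not extend the requirement to HbA1c. The cost is one sentence and one degree of freedom per model, with no new data and no change to the 140 patients.
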